**Evaluability/Non-Responders:**

**Medication Failures:** Patients who received prohibited medications or undergo unallowable corticosteroid (CS) usage will be considered “medication failures” and will be treated as non-responders at time points on and following the first date of prohibited medication or unallowable CS usage for the primary efficacy analysis. Prohibited medications are detailed in Appendix 4 of the study protocol. Prohibited medications and unallowable CS usage will be recorded as protocol deviations in the clinical database.

A patient is considered to have unallowable CS usage if any of the following is not met:

- A maximum daily dose of 30 mg/day of oral CS will be acceptable for eligibility for the study. For patients whose only SLE treatment is steroids, their stable steroid dose must be at least 10 mg/day and no more than 30 mg/day for a minimum of 6 weeks at time of randomization on Day 0
- Topical steroids may be used, but the dose must be stable for at least 6 weeks prior to Day 0, and be maintained at a constant dose throughout the study duration until the rashes resolve. PRN topical steroids are not permitted
- Once the patient has received the first dose of study drug (Day 0), tapering of oral steroids will be highly encouraged and should be continually evaluated during the protocol-allowed tapering windows (Day 0 through Day 150) with the target of achieving a CS daily dose of < 7.5 mg and < Day 0 dose between Day 150 and Day 210
- Between Day 150 and Day 210 (i.e., within 60 days of primary endpoint assessments), oral CS doses must be held constant
- CS Burst for SLE-related Indications
  - After Day 0 (first dose of study drug), a maximum of 1 oral CS “burst” equivalent to  $\leq$  40 mg/day prednisone for increased SLE disease activity will be allowed between Day 0 and Day 120, which must be tapered down to the baseline (Day 0) CS dose or lower within 14 days of initiation of the “burst”. Any “burst” continuing after Day 120 or occurring after Day 120 is considered a protocol deviation.
  - Alternatively, a single intramuscular (IM) dose of methylprednisolone ( $< 40$  mg) is permitted during this period.
- CS Burst for Non-SLE-related Indications
  - A single treatment of oral prednisone equivalent of  $\leq$  40 mg/day for 14 days is permitted for a non-SLE indication, though it must be completed prior to Day 120. No long acting steroid injections are permitted.
  - Note: Treatment with inhaled CS are allowed for the treatment of non-SLE-related indications only (e.g., for asthma).

Sponsor: Boston Pharmaceuticals, Inc.  
Protocol Number: BOS161721-02  
SAP Version and Date: Version 4.0, 23Apr2021

Any other increase from baseline of CS dose or any other systemic use of CS of any kind (including intra-articular and intravenous administration) are not permitted from Day 0 through Day 210 and will result in the patient being considered a medication failure and will be treated as non-responders for the primary efficacy analysis. There is no restriction of CS usage after Day 210.

The determination of medication failures will be reviewed using blinded data and finalized prior to unblinding. Once a patient is determined to be a non-responder, the patient will remain a non-responder for the remainder of the study.

#### **Out of Window Assessments:**

- If a patient has an efficacy assessment (i.e. BILAG, SLEDAI-2K, PGA, CLASI, etc.) more than 30 days since the previous assessment (current visit – prior visit > 30), the corresponding result will not contribute to LOCF analyses.
- Since the Day 180 nominal visit is assigned as “Day 180/End of Treatment” in the clinical database, Day 180 nominal assessments must be  $\geq$ 159 days (180 – 21 day sponsor allowed treatment window) since first dose to be considered for “Day 180” nominal assessments and also to be considered for LOCF to Day 210 in the case of missing Day 210 data for all efficacy analyses. Note, under protocol amendment 6, patients will be allowed to be treated outside of window (after consultation with the sponsor) due to the ongoing COVID-19 pandemic.

#### **Early Treatment Withdrawals/Discontinuations:**

For early treatment withdrawal/discontinuation prior to study day 159 (180 days – 21 day treatment window), patient will be considered a non-responder after the date of early treatment withdrawal/discontinuation assuming the patient was not considered a medication failure prior to or on the date of early withdrawal/discontinuation for the primary efficacy analysis.

For early treatment withdrawal/discontinuation on or after study day 159 (180 days – 21 days) such that patient has data for nominal visit Day 180 but not for nominal visit Day 210, Day 180 data will be carried forward to Day 210 for assessment of SRI-4 response.

For early treatment withdrawal/discontinuation on or after study day 159 (180 days – 21 days) such that patient does not have data for nominal visit Day 180 and Day 210, the patient will be considered a non-responder on Day 210.

For early treatment withdrawal/discontinuation on Day 210 such that patient has data for nominal visit Day 210, the Day 210 data will be used for assessment of SRI-4 response.

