### 3.3. Sample Size Considerations

Sample size in the Phase 1b part of the study is based on operational consideration.

The sample size in the Phase 2 POC study is based on the primary endpoint, SRI-4 Response at Day 210. Based on efficacy data from a recently completed study with Ustekinumabiii, where the primary endpoint was also SRI-4, the sample size in the phase 2 part of the BOS161721-02 study is set at 96 evaluable patients. In the Ustekinumab study of 102 patients, a statistically significant difference in SRI-4 response was shown in favor of Ustekinumab (62% of Ustekinumab treated patients achieved SRI-4 response vs. 33% in patients receiving placebo). The Ustekinumab phase 2 study is an appropriate comparator to BOS161721-02 because both studies share the same primary endpoint of SRI-4 response and BOS161721 and Ustekinumab have overlapping mechanisms of action (T follicular helper and Th17 cell biology).

Sponsor: Boston Pharmaceuticals, Inc.  
Protocol Number: BOS161721-02  
SAP Version and Date: Version 4.0, 23Apr2021

Approximately 110 additional patients will be randomized in a 2:1 ratio to BOS161721 versus placebo to achieve approximately 96 evaluable patients in the FAS of the phase 2 portion. This assumes 14 patients will discontinue prior to having received treatment or having completed a post-baseline efficacy measure. Enrollment and randomization will be monitored in a blinded fashion and may be increased if needed to ensure at least 96 evaluable patients are randomized into the FAS (see Section 6.1).

A total of 96 evaluable patients randomized provides 80% power to detect a treatment difference of 29% in SRI-4 response rates at Day 210, based on a targeted 2-sided significance level of 10% and using a 2-sided Pearson's chi-squared test. This assumes a response rate of 62% for BOS161721 and 33% for placebo.

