#### **Missing Data:**

- **Pre-Treatment:** If a patient is missing data during the pre-treatment period for SLEDAI-2K, PGA, or BILAG, the patient will be excluded from the primary efficacy analysis.

- **Overall SRI-4 Components:** Missing data at Day 210 for overall components for SLEDAI-2K, BILAG, and PGA will be addressed by employing a LOCF analysis within each overall component as described in Section 5.4. For example, if a patient has data for SLEDAI-2K and BILAG at Day 210 but is missing PGA at Day 210, the PGA component would employ LOCF as described in Section 5.4. If the overall component is missing from Day 180 through Day 210 and the patient is not a medication failure on or prior to Day 210 and did not withdraw/discontinue treatment prior to Day 180, the SRI-4 response at Day 210 will be considered not evaluable.
- **Individual Items Contributing to Overall SRI-4 Components:** Data collection and scoring will be performed in the clinical database for BILAG, SLEDAI-2K, and PGA. If missing individual items contributing to any of the overall components occurs for Day 210, the overall component will be recalculated per the Table 1.

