**Table 2**

| Analysis   | Analysis Population | Criteria   |
|--|---------------------|--|
| Primary Analysis

LOCF for missing data,
Medication
Failures=Non-Responder | FAS                 | 
The primary analysis of the primary efficacy endpoint will be performed based on LOCF methods for missing data.
 
 
(1) Medication failures are considered non-responders on and after the date of medication failure
 
(2) Early withdrawals/discontinuations prior to study day 159 will be considered non-responders after the date of early withdrawal/discontinuation
 
 |

|  |     |  |
|--|-----|--|
|  |     | 
 
a. If patient is a medication failure prior to withdrawal/discontinuation, patient will be considered a non-responder on and after the date of medication failure.
 
b. In case of early withdrawal/discontinuation after study day 159 but before Day 210 such that patient has Day 180 data but is lacking Day 210 data in a patient without medication failure, the Day 180 data will be carried forward to Day 210.
 
 
(3) Patients with missing Day 180 and Day 210 data without prior medication failure and without early withdrawal/discontinuation prior to study day 159 are considered not evaluable and are excluded from analysis
  |

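### The SAP gives two outcomes for a late discontinuer with no Day 180 or Day 210 data (non-responder, or excluded), so the primary result is not uniquely defined if any such patient exists

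*SAP*

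**What the plan says.** All references are to SAP Version 4.0.

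- **Section 7.1.1, Early Treatment Withdrawals/Discontinuations.** For a stop on or after study day 159, if the patient "does not have data for nominal visit Day 180 and Day 210, the patient will be considered a non-responder on Day 210". If Day 180 data exist and Day 210 data do not, Day 180 is carried forward.
- **Section 7.1.1, Table 2, Primary Analysis, item (3).** Patients who miss both visits, have no prior medication failure and are "without early withdrawal/discontinuation prior to study day 159 are considered not evaluable and are excluded from analysis".
- **Section 7.1.1, Missing Data, Overall SRI-4 Components.** If a component is missing at both visits and the patient is not a medication failure and "did not withdraw/discontinue treatment prior to Day 180, the SRI-4 response at Day 210 will be considered not evaluable".
- **Section 7.2.1 (by-visit SRI-4).** Any early discontinuer is a non-responder after the date of stopping. No day-159 cut-off is given.
- **Section 7.1.1, Out of Window Assessments.** The Day 180 visit doubles as the End of Treatment visit. An assessment at least 159 days after first dose counts as Day 180.

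The sentence introducing Table 2 describes it as a summary of the primary analysis. It gives neither the table nor the text precedence. Success is a two-sided p-value below 0.10 with the higher response rate on BOS161721.

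**The concern.** The discontinuation text keeps this patient in the denominator as a failure. Table 2 takes the patient out. Two programmers following the same SAP could therefore report different response rates, confidence intervals and p-values for the primary endpoint, and each could point to a section in support.

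Exclusion raises the response rate of whichever arm loses the patient. The conflict can thus help or hurt BOS161721, depending on where late discontinuations fall.

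**Working it through.** **1. The rules side by side.** No patient below is a medication failure.

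| Patient | Discontinuation text | Table 2, primary | Missing Data text | Section 7.2.1 at Day 210 |
|---|---|---|---|---|
| Stops day 100 | Non-responder | Non-responder, item (2) | Does not apply | Non-responder |
| Stops day 170, no Day 180 or 210 data | Non-responder | Excluded, item (3) | Read literally, does not apply (stopped before Day 180) | Non-responder |
| Stops day 185, no Day 180 or 210 data | Non-responder | Excluded, item (3) | Not evaluable | Non-responder |
| Stops day 170, End of Treatment assessment on or after 159 days | Day 180 carried forward | Day 180 carried forward, item (2)b | LOCF | Non-responder |
| Stays on treatment, misses both visits | Does not apply | Excluded, item (3) | Not evaluable | Not evaluable |

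Rows 2 and 3 are the contradiction. Row 4 is consistent within Section 7.1.1, but Section 7.2.1 departs from it. Rows 1 and 5 are consistent.

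Table 2 cannot be read as meaning only patients who stayed on treatment. Item (3) of Sensitivity Analysis 1 spares everyone who discontinued before Day 210, whereas the primary row spares only those who stopped before day 159.

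**2. The plan's own figure.** Section 3.3 says "A total of 96 evaluable patients randomized provides 80% power" and "This assumes a response rate of 62% for BOS161721 and 33% for placebo", at two-sided 10%, with 2:1 allocation. With p1 = 0.33 (placebo), p2 = 0.62, ratio k = 2 and difference d = 0.29:

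- Pooled rate = (0.33 + 2 × 0.62)/3 = 0.5233
- n(placebo) = [1.645 × √(1.5 × 0.5233 × 0.4767) + 0.842 × √(0.33 × 0.67 + 0.62 × 0.38/2)]² / 0.29² = 26.6, so 27 + 54 = 81
- With continuity correction: (26.6/4) × [1 + √(1 + 6/(2 × 26.6 × 0.29))]² = 31.6, so 32 + 64 = 96

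The stated 96 is reproduced with the correction (power 80.6% at 32 and 64; 86.2% without it). Also 96/(1 − 14/110) = 110. The check below uses 64 and 32.

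**3. Effect of the two rules.** The number of disputed patients is not in the SAP, so every count here is an assumption. If k of an arm's n patients are disputed and x respond, the rate is x/n under the discontinuation text and x/(n − k) under Table 2. The test is the uncorrected Pearson chi-square, N(ad − bc)²/(product of the four margins).

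Worked example, 35/64 vs 12/32: 96 × (35 × 20 − 29 × 12)² / (64 × 32 × 47 × 49) = 2.52, p = 0.112. With two active patients removed: 94 × (35 × 20 − 27 × 12)² / (62 × 32 × 47 × 47) = 3.03, p = 0.082.

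| Assumed case | Counted as non-responders | Excluded |
|---|---|---|
| 2 active | 35/64 vs 12/32, p = 0.112 | 35/62 vs 12/32, p = 0.082 |
| 4 active | same, p = 0.112 | 35/60 vs 12/32, p = 0.057 |
| 2 active, 1 placebo | same, p = 0.112 | 35/62 vs 12/31, p = 0.107 |
| 4 active, 2 placebo | same, p = 0.112 | 35/60 vs 12/30, p = 0.1007 |
| 2 placebo | 34/64 vs 11/32, p = 0.083 | 34/64 vs 11/30, p = 0.137 |
| 2 active, 1 placebo, near design rates | 40/64 vs 11/32, p = 0.009 | 40/62 vs 11/31, p = 0.008 |
| 3 placebo, near design rates | 40/64 vs 11/32, p = 0.009 | 40/64 vs 11/29, p = 0.027 |

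The decision changes in rows 1, 2 and 5 only. The smallest expected count in any of these tables is about 13 (29 × 42/93), so the switch to Fisher's exact test is not triggered.

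**The case against.** The strongest reply is that the group is small and the intended reading can be guessed.

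- **Size of the group.** An End of Treatment assessment at 159 days or later counts as Day 180 data and is carried forward under both rules. Only patients who stop late, miss that assessment and Day 210, and are not medication failures remain. This stands, and the group may be empty.
- **Intended reading.** The discontinuation text is the specific rule and Table 2 is only a summary. That is a reason to let the text govern. But item (3) is explicit, and the SAP does not state the precedence.
- **The Day 180 cut-off.** Because nominal Day 180 can begin at 159 days, the Missing Data text may mean the same boundary. It is at least loosely worded, but it is not certainly a third rule.
- **Sensitivity analyses.** Sensitivity Analysis 1 counts these patients as non-responders and Sensitivity Analysis 2 excludes them. Both are optional and change other rules too, so they soften the conflict without resolving it.

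A reader might also infer that exclusion favours the drug. It does so only if late losses are concentrated in the active arm; placebo losses work the other way. A reader might infer that the choice would be made after unblinding. The SAP does not schedule that: Version 4.0 followed a blinded pre-lock review, and those excluded from the primary analysis are to be listed.

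**Conclusion.** The contradiction is real, sits in the current text and concerns the primary endpoint. If at least one such patient exists, the SAP does not define a single primary result.

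The size is conditional. At 64 and 32 patients, with assumed counts, two disputed patients in one arm are enough to change the decision when the result is borderline, in either direction. Removals in the 2:1 ratio, and results near 62% vs 33%, left the decision unchanged in every case tried. The documents do not support saying that the trial's conclusion depends on this point.

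Nor does the defect show that every patient not evaluable at Day 210 should be a non-responder. Patients who stay on treatment and miss both visits are handled consistently, and changing that would be a separate choice.

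**What to change.** Before unblinding:

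1. State that the discontinuation text in Section 7.1.1 governs: a patient who stops on or after study day 159, with neither Day 180 nor Day 210 data, is a non-responder at Day 210.
2. Reword item (3) of the Primary Analysis row in Table 2 so that exclusion applies only to patients who did not withdraw or discontinue before Day 210. Item (3) of Sensitivity Analysis 1 already carries that condition.
3. Bring the Missing Data text, and the Section 7.2.1 rule as it applies at Day 210, to the same rule and cut-off. Say whether Day 180 means the nominal visit or a count of days.
4. Report the exclusion version as a sensitivity analysis.

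This costs a few sentences and a programming check. Keeping these patients in the denominator may slightly lower the response rate in an arm that has them. The sample size is unaffected.

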#### **Missing Data:**

- **Pre-Treatment:** If a patient is missing data during the pre-treatment period for SLEDAI-2K, PGA, or BILAG, the patient will be excluded from the primary efficacy analysis.

- **Overall SRI-4 Components:** Missing data at Day 210 for overall components for SLEDAI-2K, BILAG, and PGA will be addressed by employing a LOCF analysis within each overall component as described in Section 5.4. For example, if a patient has data for SLEDAI-2K and BILAG at Day 210 but is missing PGA at Day 210, the PGA component would employ LOCF as described in Section 5.4. If the overall component is missing from Day 180 through Day 210 and the patient is not a medication failure on or prior to Day 210 and did not withdraw/discontinue treatment prior to Day 180, the SRI-4 response at Day 210 will be considered not evaluable.
- **Individual Items Contributing to Overall SRI-4 Components:** Data collection and scoring will be performed in the clinical database for BILAG, SLEDAI-2K, and PGA. If missing individual items contributing to any of the overall components occurs for Day 210, the overall component will be recalculated per the Table 1.

**Table 1**

| SRI-4 Component | Method for Carrying Forward Individual Items Contributing to SRI-4 Component Result/Score  |
|------------------------|---|
| BILAG Grade            | BILAG Grading is evaluated and entered into the clinical database by the medical monitoring team. Grades are adjudicated by independent subject matter experts. The medical monitoring team and the adjudication team will utilize BILAG index results to determine BILAG Grades. Missing data will be handled by the medical monitoring team as follows. If lab values are missing in the BILAG Index at Day 210, lab values from the most recent unscheduled visit $\leq$ 14 days after Day 210 will be utilized for determination of the BILAG grade in the applicable organ system and entered into the clinical database. If lab values are not available from an unscheduled visit $\leq$ 14 days after Day 210, laboratory data will be carried forward from the most recent laboratory assessment (scheduled or unscheduled) $\leq$ 30 days prior to the Day 210 nominal visit for determination of BILAG grade. If the lab components for BILAG are missing from Day 210 and no unscheduled laboratory assessments occur within 14 days after or 30 days prior to the Day 210 assessment, the lab components from Day 180 will be utilized if Day 180 occurred within 30 days of Day 210. Otherwise, no individual BILAG Index results will be carried forward. If the BILAG grade for a given organ system is missing at Day 210, the grade will be carried forward from the Day 180 assessment. If the Day 180 BILAG grade is also missing, occurred more than 30 days before Day 210 (Day 210 visit date – Day 180 visit date > |

Sponsor: Boston Pharmaceuticals, Inc.

Protocol Number: BOS161721-02

SAP Version and Date: Version 4.0, 23Apr2021

|           |   |
|-----------|---|
|           | 30), or is not evaluable, the Day 210 grade will be considered not evaluable.   |
| SLEDAI-2K | 
If lab values are missing at Day 210, lab values will be imputed based on the below hierarchy of determination:
 
(1) If any unscheduled laboratory assessments occurred <=14 days after the Day 210 visit, the laboratory values at the most recent unscheduled laboratory assessment will be used for the determination of missing laboratory SLEDAI-2K criteria. For example, if platelet count is missing at Day 210 and an unscheduled laboratory assessment occurs 10 days after the Day 210 visit date, the platelet count from the unscheduled laboratory assessment would be used to determine if the patient had thrombocytopenia at Day 210 for SLEDAI-2K.
 
(2) Else if #1 does not occur or lab values are not available at the unscheduled visit noted in #1, the laboratory data will be carried forward from the most recent laboratory assessment (scheduled or unscheduled) <=30 days prior to the Day 210 nominal visit to make the SLEDAI-2K determination. For example, if a patient is missing thrombocytopenia and leukopenia SLEDAI-2K components at Day 210, they have an unscheduled lab assessment 10 days earlier with platelet counts populated and WBC not populated, and they have a Day 180 assessment within 30 days of the Day 210 visit with both platelets and WBC present, the platelet value from the unscheduled visit would be carried forward to the Day 210 for thrombocytopenia component designation and the WBC value would be carried forward from the Day 180 assessment to Day 210 for the Leukopenia component designation.
 
(3) If the lab components for SLEDAI-2K are missing from Day 210 and no unscheduled laboratory assessments occur within 14 days after or 30 days prior to the Day 210 assessment, the lab components from Day 180 will be carried forward, if available and if Day 180 occurred within 30 days of Day 210.
 
Otherwise, no non-lab individual SLEDAI-2K components will be carried forward. If non-lab individual components are missing at Day 210, the entire SLEDAI-2K score from Day 180 will be carried forward. If Day 180 is missing, occurred more than 30 days before Day 210, or is not
 |

|     |   |
|-----|---|
|     | 
evaluable, LOCF is not implemented and the Day 210 score will be considered not evaluable. In the case of missing SLEDAI-2K lab components at Day 210, where any SLEDAI-2K lab component is carried forward (or back) per above, the SLEDAI-2K total score will be recalculated outside of the clinical database as the sum of:
 
 
(1) All of the non-missing weights for each descriptor at Day 210
 
(2) All individual lab component weights carried forward from the Day 180 visit or unscheduled visit, as applicable.
 
 
If any components are still missing at Day 210 after carrying forward available lab components, the Day 210 SLEDAI-2K score will not be recalculated and will be considered not evaluable.
 
Note: Clinical input may be obtained prior to database lock and unblinding to make a final determination of SLEDAI-2K criteria in the case of carrying forward (or back) individual lab component scores.
 |
| PGA | 
Individual components are not applicable for PGA and will not be carried forward. Total PGA VAS measurement will be carried forward from the Day 180 visit in the case of missing PGA measurement at Day 210. If total PGA score is also missing from Day 180, occurred more than 30 days before Day 210, or is not evaluable, LOCF is not implemented and the Day 210 visit will be considered not evaluable.
   |

Table 2 summarizes the primary analysis and details several sensitivity analyses which may be performed:

